Effects of memantine (MEM) vs. placebo (PBO) on WM (%ile score from MCCB, see text). WM was increased by MEM in 7 out of 8 subjects, and unchanged in the 8th. In these subjects ($F=10.68$, $p<0.015$), MEM also significantly increased PPI. This ongoing study is conducted with a double-blind, balanced order design.

The implications of these preliminary findings are potentially quite significant, as they suggest that MEM might enhance PPI and WM, particularly among subgroups of individuals carrying "biomarkers" that include low baseline PPI, high novelty seeking, and/or the Val/Val COMT genotype. If this same pattern of results is detected in clinical populations, it will suggest a means to prospectively identify patients in whom memantine (or other putative pro-cognitive agents) can enhance specific neurocognitive abilities (e.g. WM) to synergize with therapeutic interventions (e.g. cognitive training) that rely on these abilities. We are currently planning to test this prediction in clinical populations, including patients with schizophrenia, who are enrolled in IRB-approved clinical trials of cognitive training.

Summary of Progress to Date

A. Drug Effects on Prepulse Inhibition of Startle:

1. We carefully examined the effects of 4 dopamine agonists (amphetamine, 20 mg), bromocriptine, 1.25 mg), pramipexole (0.125 and 0.175 mg) and amantadine, 200 mg) and one NMDA antagonist (memantine, 20 and 30 mg) on prepulse inhibition (PPI) and related measures, and reported on these effects in five papers (below). Paradigms were modified to increase the sensitivity to drug effects (e.g. via use of within-subject designs or optimal stimulus parameters), and new paradigms were developed to provide new insights into these drug effects (e.g. via the development of a novel sensory gating paradigm). Our findings identified quite distinct effects of these drugs in our behavioral paradigms; for example, amphetamine on the one hand, and amantadine and memantine on the other, produced opposite effects on PPI, with amphetamine significantly disrupting and amantadine and memantine significantly increasing PPI. These effects were not predicted based on our preclinical findings in rats, and have led to new hypotheses and insights related to cross-species differences in the regulation of sensorimotor gating.

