1. The "WITHIN-SUBJECT" study involves a single drug. There will be 2 test days – on the additional test day, subjects will receive either placebo or an active dose of one of the following: amphetamine (20 mg), memantine (10 mg) and memantine (20 mg). Some studies may require a venopuncture for genetic analysis as discussed above. A "model" example of a WITHIN-SUBJECT test schedule is shown below:

Test Day 1

0815-0845 Subject signs required forms, provides urine sample, eats standardized breakfast, venopuncture (if required)

0845-0900 Vital signs (VS) check, hearing and vision test, symptom rating scale.

0900-0915 drug or placebo administration.

0915-0930 VS check; symptom rating scales.

0930-0945 EMG electrodes applied.

0945-1000 VS check; symptom rating scales.

1000-1125 Startle response measurement, including PPI, habituation and intensity assessment.
1125-1140 VS check; symptom rating scales.
1140-1155 Visual LI or Visuospatial priming or MCCB
1155-1210 VS check; symptom rating scales.
1210-1300 Subject offered lunch from cafeteria.
1300-1600 VS check hourly; subject dismissed if VS within established parameters at 1600.

Test Day 2: 7-30 days after Test Day 1

0815-0845 Subject signs required forms, provides urine sample, eats standardized breakfast, venopuncture (if required)
0845-0900 Vital signs (VS) check, hearing and vision test, symptom rating scale.

0900-0915 drug mg or placebo administration: WHICHEVER DOSE WAS NOT RECEIVED ON TEST DAY 1

0915-0930 VS check; symptom rating scales.
0930-0945 EMG electrodes applied.
0945-1000 VS check; symptom rating scales.
1000-1125 Startle response measurement, including PPI, habituation and intensity assessment.
1125-1140 VS check; symptom rating scales.
1140-1155 Visual LI or Visuospatial priming or MCCB
1155-1210 VS check; symptom rating scales.
1210-1300 Subject offered lunch from cafeteria.
1300-1600 VS check hourly; subject dismissed if VS within established parameters at 1600.

Subjects will be instructed to not eat on the morning of the test, and instead will be served a standardized meal 30 min prior to drug administration, so as to maintain a controlled and consistent impact on drug absorption.

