No drugs will be used in studies with subjects < 18 years of age. Nonetheless, it is reasonable to ask whether these drugs have been used safely in 18-35 year old subjects (or, in the case of memantine, 18-45 year old subjects). Although dopamine agonists have primarily been used and tested in Parkinsonian patients, some of these dopamine agonists are used in children. Amphetamine is used safely and effectively in children with Attention Deficit Disorder. The only drug in this proposal that does not have a specific indications or common use in adolescents is memantine. We have published findings of memantine's safe use in 18-35 year old study subjects, as described above. The fact that memantine is most often used in patients with multi-system medical illness (Alzheimer's Disease) accounts for some of its rare but more significant side effects (e.g. hallucinosis).

i. Laboratory Measures:

1. Startle Reflex: The startle reflex will be measured in control populations in men and women to examine sex differences in the startle-facilitating and inhibiting effects of weak and strong prepulses presented at short and long prepulse intervals. Sex differences in prepulse modulation of startle also will be measured using cross-modal stimuli (acoustic prepulse and tactile pulse). Sensorimotor inhibition and facilitation will be measured in women during different phases of the menstrual cycle.

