j. Statistics: Tests for homogeneity of variance are performed, and if appropriate, analyses of variance (ANOVA) used. Statview/Superanova software is used on the Macintosh. For startle data, P-Alone amplitude, PPI and startle latency are analyzed by ANOVAs; for drug studies, drug dose is used as a within-subject factor. Habituation is detected by a significant effect of trial block. Visuospatial priming is analyzed separately for baseline, facilitation, and inhibition conditions using ANOVAs. Baseline is a measure of visuospatial response time, while facilitation and inhibition scores are measures of sensorimotor modulation. Nonparametric statistics are used for the Latent Inhibition analyses because data from this test tend toward a bimodal distribution. A rank sum factorial analysis is used for the data. Other dependent measures will be analyzed with parametric or non-parametric analyses, generally consisting of mixed design ANOVAs, as appropriate. Following a significant ANOVA, specific comparisons are made using Tukey's tests. Alpha is 0.05.

Power considerations: Sample sizes vary across the different studies, based on issues ranging from the study design and goals to empirical evidence for effect sizes with the proposed drug or measure. For example, "ONE-DAY" studies are designed to identify and "pilot" optimal stimulus parameters for testing specific hypotheses, and these studies may not be powered to achieve traditional levels of statistical significance. On the other hand, designing studies of drug effects on PPI and related measures in control or patient populations requires detailed power information.

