Recruitment of female subjects: As per NIH guidelines, it is important to establish whether observed drug effects on these psychophysiological measures are sex-specific. Our current NIMH application thus proposes the use of female subjects in within-subject studies of drug effects on PPI, LI and related measures. At present, approval for studies in females is sought only for studies with amphetamine and memantine. Methods for these studies will be identical to those described above for male subjects, with the following exceptions: 1) urine pregnancy tests ("Surecheck Early Pregnancy Test") will be completed at the time of initial screening and test day 2 (exclusion: positive test); 2) testing will occur only during post-menses days 1-10; 3) blood will be drawn on the morning of testing and stored for possible later hormonal analyses using the GCRC/CTRI laboratory services; a total of 5 cc will be collected by venopuncture using GCRC/CTRI or hospital phlebotomy services.

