For the drug evaluation study, the proposed drugs carry a very small risk of toxicity or adverse side effects in the doses to be used in this study. The most common side effects associated with each drug are listed in Section 8 above, and typically include nausea, somnolence and dizziness. We do not plan to administer these drugs to subjects in whom it is contraindicated, such as subjects with known cardiovascular or neurological disorders. The doses selected for use in these studies are in the low- or below-therapeutic range for these drugs when they are used clinically, and in most cases, the selected dose is equal to or less than the lowest recommended starting clinical dose for the drug. To address the potential for some of these drugs to produce changes in blood pressure, we will carefully monitor subjects' vital signs, and will not release subjects from the hospital until their vital signs are within normal limits. To address the possible side effect of somnolence, we will instruct subjects to arrange for their transportation from the hospital on test days. For studies that include women of childbearing potential, there is the possibility of unforeseen harm to an unborn child due to the administration of drugs. To address this risk, all female subjects will be asked to provide a urine sample to test for pregnancy and we will exclude participants who test positive. Additionally, all female subjects in these studies will be required to use a non-drug birth control method, such as abstinence, diaphragm, non-hormone intrauterine device to prevent pregnancy during the study. Subjects will be told to report if their menstrual cycle is inconsistent or if suspect that they are pregnant. Drugs will be dispensed by a licensed physician, and a licensed physician will be present on the premises at all times during testing. The consent forms include the related risks specific to the drug it refers to.

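### The 7-30 day gap and the post-menses day 1-10 window are not coordinated, so women's two test days can fall at different cycle days, and the analysis adjusts for neither cycle day nor test order

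*Protocol*

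**What the plan says.** Protocol section 9.g (within-subject test schedule) has two test days, one on active drug and one on placebo. The second day gives "WHICHEVER DOSE WAS NOT RECEIVED ON TEST DAY 1", and its timing is "Test Day 2: 7-30 days after Test Day 1". The schedule is offered as a model example.

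Protocol section 11, on recruiting women, states: "Methods for these studies will be identical to those described above for male subjects, with the following exceptions". Three exceptions follow: pregnancy tests, the rule that "testing will occur only during post-menses days 1-10", and blood stored on test mornings for possible hormone assays. None of them alters the 7-30 day gap, so both limits bind women. No sentence asks for the two visits to be at a similar cycle day, or says whether they belong in one cycle or two. Section 14 adds that "all female subjects in these studies will be required to use a non-drug birth control method", so cycles are not fixed by hormonal contraception.

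On analysis, protocol section 9.j says "for drug studies, drug dose is used as a within-subject factor". The factors named there and in the SAP are drug or dose, prepulse interval, cognitive domain, diagnosis, basal PPI level and genotype. Cycle day and test order are not among them. On order, section 8 says of the memantine study in controls: "This ongoing study is conducted with a double-blind, balanced order design". This is not restated for the amphetamine study or the schizophrenia study.

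**The concern.** In a two-day crossover each woman is her own control, and anything that differs between her two days goes into her drug-placebo difference. A window on cycle day limits that source of variation, but a minimum gap of 7 days inside a 10-day window pushes same-cycle visits towards opposite ends of it. The 30-day cap then restricts how far the next cycle can be used instead. If PPI or cognition drifts over those days, the drift becomes noise in women's differences. It would become bias if order were unbalanced among women. Separately, women with long cycles may find that no second visit satisfies both rules. They would then be lost or become protocol deviations, whether or not cycle day affects PPI.

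**Working it through.** The documents give no figure on cycle timing to reproduce, so the check enumerates the permitted day pairs.

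**Inputs from the protocol.** Gap of 7-30 days (section 9.g); both visits on post-menses days 1-10 (section 11).

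**Assumption.** Cycle length L is not given. It is taken as the interval between successive post-menses day 1s and is varied.

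**Same cycle.** With visits on days a and b, 7 ≤ b − a is required. Only six pairs qualify: (1,8), (1,9), (1,10), (2,9), (2,10) and (3,10). All are 7-9 days apart, and the first visit must be on day 1, 2 or 3.

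**Next cycle.** The condition is 7 ≤ L + b − a ≤ 30, so b − a ≤ 30 − L. An exact match (b = a) needs L ≤ 30. For L from 21 to 30 it is available from every starting day.

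| L (days) | Next-cycle pairs | Closest next-cycle match (days) | Within 2 days, of all pairs | First-test days with no permitted second visit |
|---|---|---|---|---|
| 28 | 72 | 0 | 44 of 78 | none |
| 30 | 55 | 0 | 27 of 61 | none |
| 31 | 45 | 1 | 17 of 51 | none |
| 32 | 36 | 2 | 8 of 42 | none |
| 33 | 28 | 3 | 0 of 34 | none |
| 34 | 21 | 4 | 0 of 27 | day 4 |
| 35 | 15 | 5 | 0 of 21 | days 4-5 |
| 40 | 0 | none | 0 of 6 | days 4-10 |

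**Bias.** Let c be the mean shift from first to second visit and p the share of women given active drug second. The mean drug-placebo difference moves by c(2p − 1), which is 0 at p = 0.5 and 0.2c at p = 0.6.

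**Variance under balanced order.** Assume a linear drift of δ SD over the 9 days from day 1 to day 10, and between-day correlation ρ. A pair k days apart carries a shift of δk/9. The variance of the difference without drift is 2(1 − ρ) in SD² units, so the relative increase is (δ²/81) × mean(k²) / [2(1 − ρ)]. With ρ = 0.6 the denominator is 0.8. δ²/0.8 is then 0.1125 at δ = 0.3 and 0.3125 at δ = 0.5.

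- Same-cycle pairs: mean k² = (3×49 + 2×64 + 81)/6 = 356/6 = 59.3, and 59.3/81 = 0.733. The increase is 0.733 × 0.1125 = 8% to 0.733 × 0.3125 = 23%.
- All 78 pairs at L = 28, equally likely: the next-cycle pairs contribute Σk² = 866 and the same-cycle pairs 356. Mean k² = 1222/78 = 15.7, and 15.7/81 = 0.193. The increase is 2.2% to 6.0% in women.
- If half the subjects are women: 1.1% to 3.0% overall.
- If δ = 0: no increase.

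**The case against.** The strongest reply is that little is shown to be lost. The documents give no cycle-day effect on PPI or cognition, no between-day correlation, no cycle length and no share of women, so every driver of the variance figures is assumed. Section 9.c describes most studies as male only, which makes half women a generous case. The 7-30 day gap sits in a model schedule and may be applied flexibly. Stored blood offers a possible route to later adjustment. For cycles up to 30 days, staff can already book matched days. All of this stands and keeps the point small. It does not remove the gap: matching is not asked for, hormone assays are only possible, and no planned model uses them.

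A reader might go further and infer that menstrual phase confounds the drug effect. The documents do not support that. Both visits lie in one 10-day window, so what varies is cycle day, by at most 9 days, and nothing shows that a phase boundary is crossed. Section 9.i.1 does say "Sensorimotor inhibition and facilitation will be measured in women during different phases of the menstrual cycle", but that text concerns startle and sex differences in control populations. It does not show that PPI moves over post-menses days 1-10. The purpose of the window is also unstated.

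A reader might also apply the full end-to-end shift to every woman, giving 11-31% in women (0.1125 and 0.3125 above) and about 6-16% overall if half are women. That contradicts the enumeration. At a 28-day cycle 44 of 78 permitted pairs are within 2 days, and only 12 of 78 are 7 or more days apart.

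**Conclusion.** The point holds as a modest one about coordination and precision. A difference of 7-9 cycle days is unavoidable when both tests fall in one cycle. Some difference is unavoidable at any cycle length above 30 days. At 30 days or less it is avoidable but not guarded against. From 34 days the two rules leave some women without a permitted second visit, which needs resolving whatever the effect on PPI.

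Under balanced order the cost is precision in women, not bias. On the stated assumptions it is about 2-6% of variance in women, 1-3% overall with half women, and 8-23% in women tested twice in one cycle. The equal-likelihood assumption counts calendar combinations, not actual bookings, so the true mix could be better or worse. Because balance is stated only for the memantine study in controls, unbalanced order among women cannot be ruled out elsewhere, but nothing in the documents shows it.

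**What to change.** - Reconcile the 7-30 day gap in section 9.g with the post-menses window in section 11 for cycles longer than 30 days. How to do so is for the investigators.
- Within the windows already allowed, prefer two test days at a similar post-menses day where that is possible.
- Record post-menses day at each test.
- In the women's analysis, include test order and the signed cycle-day difference (active day minus placebo day) for all women. The sign matters, because the direction of any shift in the drug-placebo difference depends on which day carried the drug. An unsigned difference, or a term that enters only above some threshold, would not remove it.
- State whether order is balanced among women in each study.

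The cost is small: one recorded number per visit and one or two degrees of freedom. Some women would return in the next cycle rather than after a week, with some added risk of dropout. The SAP already reports results, so the booking preference helps only remaining or future testing. Adjustment is still possible for completed data where post-menses day can be recovered.

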Vital sign assessment during and after testing will be performed in lying, sitting and standing positions, by a trained researcher or health professional. Sessions will be discontinued for $55 > HR > 110$, $90 > SBP > 160$, $45 > DBP > 95$, emesis, severe discomfort or other unanticipated medical or psychological consequence. At the end of testing, at the times described above, subjects will be dismissed if their heart rate is between 55 - 90, their SBP is between 90 - 150, their DBP is between 45 - 90, and there is no evidence of dizziness or significant heart rate increase or blood pressure reduction on postural changes, from lying to sitting to standing.

2. The "ONE-DAY" test session: When developing new test sessions, we often examine correlations between response characteristics elicited by different stimulus parameters. The subjects participating these types of studies will be tested with air puff and all acoustic stimuli. Acoustic stimuli will be no louder than 118 dB(A), a level already approved in previous protocols (most recently 071154). No drugs are administered during these studies.

These studies will include up to 50 normal control subjects per year. Some subjects may be screened on the phone and in person, as done in previous studies. The consent form used will have the different possible tests listed. The options are:

1. A urine test will be required to test for the presence of illicit drug use. Your study participation will be terminated if the urine test is positive for any drugs, and you will be paid for your time, which will be prorated as stated below. Only the researcher will know the results of the test. This procedure takes approximately 10 minutes.
2. You will be asked to fill out several personality questionnaires. You can skip any questions you do not want to answer. This procedure takes approximately 30 minutes.
3. You will be given a psychiatric examination that includes medical, psychiatric, social and drug histories. This procedure takes approximately 20 minutes.

4. Eyeblink startle: two electrodes with adhesive backing will be placed next to both eyes so that your blink reflex can be measured, and one will be placed behind the left ear as a reference measure. This procedure takes approximately 10 minutes. The procedures listed below may occur concurrently.
5. You will be asked to complete one or more computer task(s), each approximately 15 to 20 minutes.

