Medications are administered in the UCSD Clinical Teaching Facility, rooms A-304A and A305, which are staffed by a physician or registered nurse. To date, amphetamine as a single 20 mg oral dose has been administered to 65 subjects in our studies, 49 in a within-subject double-blind placebo-controlled study, and 16 in a between-subject double blind study. No subjects reported adverse effects of this dose of amphetamine. Measures of autonomic function indicated the expected increases in heart rate and blood pressure after amphetamine, as indicated below. However, in each case, these increases were numerically small (see Table 1) and did not approach levels that would normally be of medical consequence in a healthy young adult population. Only one subject exhibited a heart rate with amphetamine in excess of 100; several placebo subjects exhibited heart rates in the 90's.

Table 1. Autonomic effects of 20 mg d-amphetamine po in 65 subjects tested to date

	Placebo	Amphetamine
Ave. Heart Rate during test session (mean (SEM))	66.55 (1.24)	68.92 (1.14)

Maximum HR (mean (SEM))	73.27 (1.40)	75.94 (1.49)
SBP (mean (SEM))	113.15 (1.74)	116.65 (1.54)
DBP (mean (SEM))	67.23 (1.01)	70.02 (0.86)

Subjective ratings also demonstrated no adverse effects of this drug dose, based on visual analog scale (VAS) self-assessments (Table 2). In these scales, 0 = no effect, 100 = extreme effect. Other scales indicated that this dose of d-amphetamine reduced drowsiness, and was associated with a trend towards an increased sense of being "happy".

Table 2. VAS scores for subjective effects of 20 mg d-amphetamine po in 65 subjects tested to date

	Placebo	Amphetamine
Dizzy (mean (SEM))	2.73 (0.68)	3.04 (0.76)
Queasy (mean (SEM))	2.10 (0.52)	1.78 (0.30)

Summary: A 20 mg po dose of amphetamine is used commonly in the published literature in studies of normal, healthy adults, without common adverse reactions. This experience is validated in our own studies of 65 normal adult subjects.

References are included at the end of this section.

Memantine is the only drug in this application that is being proposed for testing in schizophrenia patients. It is FDA-approved for the treatment of dementia, but has been widely used in a number of different clinical conditions (see below).

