For example, to assess the effects of memantine on "gating" measures in schizophrenia patients, the primary measure will be evaluated by 2-way repeated-measure ANOVA of PPI with memantine dose and prepulse interval as within-subject factors. The hypothesis that memantine will increase PPI in schizophrenia patients will be confirmed by a significant effect of dose (active > PBO) or significant dose x interval (int) interaction and post-hoc comparisons at one or more prepulse intervals. Existing data (see above) provide a strong *a priori* prediction that the 120 ms prepulse interval will be most sensitive to PPI-enhancing effects of MEM. The effect size (d) for PPI-enhancement by 20 mg memantine in HCS was 0.91; with a similar "d" in patients, 30 patients/dose yields power of 0.92 to detect the predicted memantine effects; with maximum expected attrition (n=24), power is 0.85. Past findings also lead to the prediction that these MEM effects would be most robust in subjects exhibiting the lowest basal PPI levels (d=1.80). Using a median split of mean basal (screening) PPI levels, ANOVA as above will detect a significant interaction of memantine dose x basal PPI level, or dose x basal level x int, and significant post-hoc comparisons at one or more prepulse intervals (again, 120 ms being the strongest *a priori* candidate). Given the published "d" in control subjects, a comparable "d" in the proposed 12-15 "low PPI" patients/dose group would yield power >0.95 to detect the predicted memantine effects.

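### The three vital-sign limits for stopping a test session are written as inequalities that no value can satisfy, so as printed they never trigger

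*Protocol*

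**What the plan says.** Protocol section 9.g (Test schedules) follows the model within-subject schedule with a paragraph on vital signs, which are measured lying, sitting and standing, during and after testing. It gives this rule for ending a session: "Sessions will be discontinued for $55 > HR > 110$, $90 > SBP > 160$, $45 > DBP > 95". The same sentence then adds triggers without numbers: vomiting, marked discomfort, and other unexpected medical or psychological events.

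The next sentence sets the conditions for release at the end of the day: "subjects will be dismissed if their heart rate is between 55 - 90, their SBP is between 90 - 150, their DBP is between 45 - 90", together with the absence of dizziness and of marked postural changes.

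Section 9.h gives background data under the heading "Table 1. Autonomic effects of 20 mg d-amphetamine po in 65 subjects tested to date". The placebo session-average heart rate is 66.55 (SEM 1.24). The text describes the 65 as "49 in a within-subject double-blind placebo-controlled study, and 16 in a between-subject double blind study" and comments on individual heart rates only at the high end: "Only one subject exhibited a heart rate with amphetamine in excess of 100; several placebo subjects exhibited heart rates in the 90's". It does not mention low heart rates or sessions stopped for vital signs.

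**The concern.** A stopping rule has to be something that the person taking the reading can apply without interpretation. In a chained inequality both parts must hold together. The three chains in section 9.g each set the lower number as a ceiling and the upper number as a floor, so the two parts exclude one another.

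At stake is whether the numeric part of the rule does anything. Someone applying it exactly as printed, or programming it into a data check, would never see it fire, however extreme the reading. Two staff members who each supply their own interpretation have no text to settle a difference. The rule governs sessions in which amphetamine or memantine is given, so this is operative text and not background.

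**Working it through.** **Step 1. The logic of the printed rule.** A condition of the form a > x > b means x < a and x > b. Some value can satisfy it only if b < a.

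| Measure | a (must be below) | b (must be above) | Is b < a? | Values that satisfy it |
|---|---|---|---|---|
| Heart rate | 55 | 110 | No | None |
| Systolic pressure | 90 | 160 | No | None |
| Diastolic pressure | 45 | 95 | No | None |

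A search in steps of 0.1 from 0 up to 300 also found no value meeting any of the three conditions.

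**Step 2. What was probably meant.** Set the stop numbers beside the dismissal ranges:

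| Measure | Stop, lower | Stop, upper | Dismissal range |
|---|---|---|---|
| Heart rate | 55 | 110 | 55-90 |
| Systolic pressure | 90 | 160 | 90-150 |
| Diastolic pressure | 45 | 95 | 45-90 |

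The lower numbers are identical in all three rows. The upper stop numbers exceed the upper dismissal numbers by 110 - 90 = 20, 160 - 150 = 10 and 95 - 90 = 5. If the rule means x < a or x > b, the two sets nest: a reading between the two upper numbers would neither end the session nor allow release, and a reading below the lower number would do the first and prevent the second. Simply reversing the signs would instead stop sessions for readings inside the limits, which makes no sense beside the dismissal ranges. So outside the limits is the evident intent, though it is inferred and not stated. Values exactly at a limit are also unsettled: the stop signs are strict, and the dismissal wording does not say whether its endpoints count.

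**Step 3. Side note: how the lower heart-rate number sits against Table 1.** The plan states no stopping rate, so there is no figure to reproduce. Inputs from Table 1 are a placebo mean of 66.55 and an SEM of 1.24. The placebo n is not given. Two candidates are 49 (the crossover subjects) and 65 (the number in the table title). With SD = SEM × √n and P(average < 55) = Φ((55 - 66.55)/SD):

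- n = 49: SD = 1.24 × 7 = 8.68; z = -11.55/8.68 = -1.33; P = 0.092.
- n = 65: SD = 1.24 × 8.06 = 10.00; z = -11.55/10.00 = -1.155; P = 0.124.

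Other shapes with the same mean and SD, giving the value for n = 49 and then n = 65:

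- Lognormal: 8.0% and 11.5%.
- Gamma: 8.5% and 11.9%.
- Right skewness of 1.0 (shifted gamma): 4.7% and 9.2%.
- Right skewness of 1.5 (shifted gamma): about 0% and 4%.

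A mean and an SEM do not fix the lower tail.

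**The case against.** The strongest reply is that this is a slip of notation and nothing more. The matching lower limits in the next sentence make the intent plain, any clinician would read the rule as outside the limits, a licensed physician is on the premises during testing, and nothing in either document shows that staff misread it. All of that stands, and it keeps the point small. It does not make the printed conditions workable, and the dismissal ranges show that a plain form was at hand.

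Three stronger inferences are tempting, and the documents do not support them.

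- **That no session could ever be stopped.** The non-numeric triggers in the same sentence work as written. Only the vital-sign limits fail.
- **That the intended lower heart-rate limit would stop about one in ten healthy placebo subjects by the protocol's own data.** Table 1 holds a mean and an SEM, not a count of low readings. The figure needs an assumed n and an assumed shape. It also describes session averages, whereas the rule applies to readings taken during the session. The spread can be checked only at the other end. With n = 65, the maximum-heart-rate row predicts about 4.5 placebo subjects above 90 and 1.5 amphetamine subjects above 100. That is compatible with the text, but it says nothing about the lower tail. Nor does a mean of 66.55 contradict a cautious limit, whose choice is a clinical matter.
- **That such stops would use up the attrition allowance behind the stated power.** The allowance, "with maximum expected attrition (n=24", belongs to the memantine study in schizophrenia patients. Table 1 comes from healthy volunteers in amphetamine studies, and section 9.j does not say which losses its allowance covers.

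The documents also do not say how data from a stopped session would be analysed. That is a missing detail, not an error in this rule.

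**Conclusion.** The point holds as a wording defect in an operative safety rule. All three of the three numeric stop conditions are impossible to meet as printed. This rests on no assumption, since it follows from the inequalities alone. That outside the limits was meant is an inference from the shared lower numbers, a strong one, and it leaves the authors to confirm it.

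The 9-12% is context only. It assumes approximate normality and a placebo n between 49 and 65, and it falls well below that range if the distribution is markedly right-skewed. It shows neither that the limits are wrong nor that any session was lost, and nothing about power follows from it.

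**What to change.** Restate each of the three limits as two separate one-sided conditions, below the lower limit or above the upper limit, with the word or written out. Say whether a reading exactly at a limit counts. In the same edit, have the clinical team confirm that this is what was meant and that the stop and dismissal limits are consistent with each other. The values are theirs to set, and none is proposed here.

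The cost is one sentence in section 9.g and a short clinical check; design, sample size and analysis are untouched. The SAP already reports memantine results, so for sessions already run the wording cannot be changed in retrospect. A line in the study report saying how staff applied the limits would be enough.
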